ClinicalTrials.gov ID: NCT05419557,

Unique Protocol ID: U21-12-4630

Official Title: Buen Provecho!: A Virtual Family-Based Intervention to Promote Health

Brief Title: Buen Provecho!: A Virtual Family-Based Intervention to Promote Health

Document dates:

Protocol: uploaded to clinicaltrials.gov 02/07/2023, Approved by IRB
07/31/2022

Informed consents: uploaded to clinicaltrials.gov 02/07/2023, Approved by IRB
07/31/2022

Protocol ID: U21-12-4630

Title of Research Protocol: *Buen Provecho!: A Virtual Family-Based Intervention to Promote Health*

Principal Investigator(s)

Inova Loudoun Hospital
[name], MPH, RN

HealthWorks Northern Virginia
[name] [name], MS, FAAP

Sub-Investigator(s)

Inova Health System
[name]

HealthWorks for Northern Virginia
[name]

Sponsor

National Center for Advancing Translational Sciences of the National Institutes of Health
under Award Number UL1TR003015

Site of Investigation
HealthWorks for Northern Virginia

Date of Protocol

July 21, 2022

Table of Contents

Abstract	3
Aims & Hypothesis	4
Background	4
Study Design	6
Recruitment	7
Study Methods & Procedures	8
Data Analysis	9
Human Subjects Protection	10
List of Abbreviations	15
Appendix A: Study Flow Chart	16
Appendix B: Recruitment Flyer	17
Appendix C: Survey	18

ABSTRACT

Title: Buen Provecho!: A Virtual Family-Based Intervention to Promote Health

Short Title: Buen Provecho Virtual Intervention

Rationale: Obesity rates are significantly higher among Hispanic youth in the United States, disproportionately putting these children at an increased risk for obesity-related diseases such as hypertension, dyslipidemia, and impaired glucose tolerance. While virtual programming offers an innovative option for pediatric weight management, limited data exists on the efficacy of virtual interventions for this population and their guardians (parents / caregivers).

Objectives: The purpose of this pilot study is to compare the effectiveness of an expanded virtual educational program (expanded –Inova Healthy Plate Club, x-IHPC) at modifying knowledge, self-efficacy, and behaviors when compared to traditional in-office counseling for guardians of children who are obese or overweight.

Study Design: In order to test the effectiveness of the x-IHPC intervention, outcomes from participants in this pilot study will be compared with outcomes from a comparison group of similar participants who receive standard nutrition counseling during their regularly scheduled check-ups. The team will enroll 25 children in the x-IHPC intervention and the same number in the comparison group (n=50). Both groups will receive standard in-office counseling, but the intervention group will also receive the x-IHPC.

Study Methodology: The comparison group receives standard, in-office counseling at visits 1, 3-months and 6-months. The intervention group receives standard in-office counseling at the same intervals, and also participates in a 12-week x-IHPC developed by a dietitian curriculum specialist. In addition, a key pillar of this study is identifying and training Community Health Workers (CHWs) to be Spanish-speaking facilitators of the x-IHPC and utilizing community engagement strategies. Training these CHWs and including them in designing the x-IHPC curriculum, will ensure that the programming is culturally appropriate; includes local features that relate directly to the community's needs; and enables study facilitators to respond effectively to the questions and learning needs of the parents and children involved in the program.

Statistical Methodology:

To examine the research question, a longitudinal analysis using generalized estimating equations (GEE) will be conducted to assess if mean differences exist on dietary measures, screen time, physical activity and guardian self-efficacy and confidence between the intervention and comparison groups while accounting for the correlation among the repeated measurements and controlling for covariates.

1. INTRODUCTION

1.1. Specific Aims

Obesity rates are significantly higher among Hispanic youth in the United States, disproportionately putting these children at an increased risk for obesity-related diseases such as hypertension, dyslipidemia, and impaired glucose tolerance. Despite this disparity, there is a lack of literature pertaining to culturally relevant and family-centered interventions for Hispanic youth and their families. While virtual programming offers an innovative option for pediatric weight management, limited data exists on the efficacy of telehealth /virtual interventions for this population and their guardians.

The purpose of this community-engaged quasi-experimental study is to determine whether a family-based, culturally tailored, virtual intervention enables guardians to shape the weight-related aspects of their home environments and the lifestyle behavioral practices (diet, exercise, screen behaviors) to be more supportive of their family's optimal health and weight, compared to standard in-office counseling alone. Specifically, the study intends to compare the effectiveness of an expanded virtual educational program (x-IHPC) at modifying knowledge, self-efficacy, and behaviors when compared to traditional in-office counseling for guardians of children who are obese or overweight.

1.2. Hypothesis

Research Question: Among guardians of children ages 6-12 years who are obese or overweight, does a family-based, culturally-tailored, virtual intervention change knowledge, self-efficacy, and behaviors about modifiable lifestyle practices to promote healthy eating when compared to standard in-office counseling?

Ho: A family-based, culturally-tailored, virtual intervention does not significantly change knowledge, self-efficacy, and behaviors about modifiable lifestyle practices when compared to standard in-office counseling.

Ha: A family-based, culturally-tailored, virtual intervention does significantly change knowledge, self-efficacy, and behaviors about modifiable lifestyle practices when compared to standard in-office counseling.

1.3. Background and Significance

Childhood obesity has been an epidemic in the United States for a generation. The national childhood obesity rate has been rising for decades putting millions of children at greater risk for Type 2 diabetes, high blood pressure, asthma, and other serious conditions.^{1,2} Recent data show that 15.5% of youth ages 10 to 17 have obesity. More importantly, the data exposes persistent racial and ethnic disparities with rates significantly higher among Hispanic youth than among White or Asian youth.³ The high prevalence of obesity among Hispanic children contributes to disparities in obesity-related disease risk factors including hypertension, dyslipidemia, and impaired glucose tolerance. It also puts them at risk for chronic comorbidities in adulthood.

Centers for Disease Control and Prevention (CDC) Growth Charts are used to measure the size and growth patterns of children and teens in the United States, with BMI-for-age weight status categories and corresponding percentiles. In children, BMI percentile cutoffs for obesity are intended to reliably define a level above which a child is more likely to have or be at risk of developing obesity-associated adverse health outcomes or diseases. Children are considered overweight at the 85th to less than the 95th percentile. Children are considered obese at the 95th percentile or greater.⁴

¹ QuickStats: Prevalence of Obesity and Severe Obesity Among Persons Aged 2–19 Years — National Health and Nutrition Examination Survey, 1999–2000 through 2017–2018. *MMWR Morb Mortal Wkly Rep* 2020;69:390.

DOI: <http://dx.doi.org/10.15585/mmwr.mm6913a6>

² Mohanan S, Tapp H, McWilliams A, Dulin M. Obesity and asthma: pathophysiology and implications for diagnosis and management in primary care. *Exp Biol Med* (Maywood). 2014;239(11):1531–40.

³ HRSA. (2019). National Survey of Children's Health (NSCH). Accessed August, 2021. <https://mchb.hrsa.gov/data/national-surveys>

⁴ CDC. (2020). <https://www.cdc.gov/obesity/childhood/defining.html>.

Recent research is exposing the connection between obesity and COVID-19.⁵ The CDC includes obesity as one of the underlying conditions that increases risk of severe illness from COVID-19.⁶ People with obesity tend to become sicker, are more likely to be hospitalized, and are even more likely to die with COVID-19 infection.⁷ COVID-19 has also disproportionately impacted people of color and impoverished communities. Hispanic people have higher rates of infection and are more than three times as likely to die from COVID-19 as are White people. Risks of severe illness are also worse for children; Black and Hispanic children are much more likely than their White peers to be hospitalized because of COVID-19.⁸

Given this high prevalence of childhood obesity and persistent racial/ethnic and socioeconomic disparities, there is an urgent need to find solutions to provide intensive, family-based pediatric weight management. Without such interventions, the chronic pandemic of obesity will continue to be exacerbated, particularly among disproportionately burdened populations.⁹ Ensuring populations affected disproportionately by obesity benefit from preventive strategies remains one of the most pressing unmet challenges in community health policy and practice.¹⁰

While obesity is a function of biology and genetics, the role of social, environmental, and economic factors in the epidemic are equally important. Experts suggest offering virtual obesity-prevention programming as a needed solution for the complex management of childhood obesity.¹¹ Providing culturally-tailored, targeted virtual programming allows children and families to have access to high quality obesity-reduction programming in their homes in a convenient and an accessible way to increase health equity. However, there is a lack of literature pertaining to culturally relevant, family-centered interventions for Hispanic youth and their families.¹² While evidence supports the use of telehealth or mobile health interventions as adjuncts to pediatric weight management as being feasible and cost-effective, limited data exists on the efficacy or effectiveness of exclusive telehealth for pediatric weight management.^{9, 11} Therefore, the purpose of this project is to test a virtual program targeting modifiable weight-related lifestyle factors for Hispanic children and their families in Loudoun County, Virginia through a community-engaged partnership between HealthWorks for Northern Virginia (HWNV) and Inova.

1.4. Preliminary Studies

None

2. STUDY DESIGN AND SUBJECT SELECTION

2.1. Study Type

Quasi Experimental: Behavioral Intervention with convenience sampling. In order to test the effectiveness of the x-IHPC intervention, outcomes from participants in this pilot study will be compared with outcomes from a comparison group of similar families who receive standard nutrition counseling during their regularly scheduled check-ups at HWNV. The team will enroll 25 children in the x-IHPC intervention and the same number in the comparison group (n=50). Both groups of children and guardians will receive standard in-office counseling, but the intervention group will additionally receive the x-IHPC (See study flowchart, Appendix A).

2.2. Setting/Location

Standard health counseling will take place during regularly scheduled office visits at the HWNV offices. The x-IHPC intervention is virtual and participants will engage in the intervention from their homes via virtual sessions.

2.3. Duration of Study

Participants will be part of the study for 6 months. This includes study recruitment, consenting, initial and subsequent in-office counseling, and x-IHPC for families enrolled in the intervention.

2.4. Number of Subjects

The team will enroll 25 children in the x-IHPC intervention and the same number in the comparison group (n=50).

2.5. Study Population

2.5.1. Gender of Subjects

There are no restrictions on the gender of the participants for this program.

2.5.2. Age of Subjects

The primary parent /guardian participating in the study is required to be over the age of 18 years.

2.5.3. Racial and Ethnic Origin

The x-IHPC program is designed to address the cultural needs of self-identified Hispanic families in our community related to the family features that impact health. Any family is eligible to participate who identifies as Hispanic and Spanish is one of the primary languages spoken in the home.

2.5.4. Vulnerable Populations

¹³ Berge, J. M., & Everts, J. C. (2011). Family-Based Interventions Targeting Childhood Obesity: A Meta-Analysis. *Childhood Obesity; Child Obes*, 7(2), 11-121. <https://doi.org/10.1089/chi.2011.07.02.1004.berge>

¹⁴ Yavuz, H. M., van Ijzendoorn, M., Mesman, J., & van der Veen, S. (2015). Interventions aimed at reducing obesity in early childhood: a meta-analysis of programs that involve parents. *Journal of Child Psychology and Psychiatry; J Child Psychol Psychiatr*, 56(6), 677-692. <https://doi.org/10.1111/jcpp.12330>

This study intervention is designed for Hispanic families in our community. The primary guardian of children between 6-12 years who screen eligible to be part of the intervention will be the individuals giving consent for their family to be part of the intervention as well as the individual providing data for the study through surveys about family and child behaviors. It is possible that some of these guardians may be pregnant at the time of consent or become pregnant during the study. Because the focus of the study is healthy eating and modifying lifestyle behaviors to improve health, the study intervention (surveys, healthy eating activities, and counseling) pose no more than minimal risk to this vulnerable group. Although children are also considered a vulnerable group, the study activities pose minimal or no risk to the children involved in the intervention.

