2.8. Exclusion Criteria

Exclusion criteria include:

1. Family plans to change location within the year
2. During initial screening for the study, the study PI determines that the intervention may exacerbate existing medical conditions of the child or the family.

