3.4.3. Secondary outcomes

BMI percentile of children and guardians enrolled in the study. This will be measured at each office visit by a trained medical assistant or the physician.

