3.5. Consent/Accent

Once a guardian has been screened as eligible for inclusion in the study, they will be approached by the physician PI and asked if they are interested in being part of the study. If they are interested, the PI will discuss whether they are interested in joining the comparison group or the intervention group. A member of the study team will meet with the family virtually or in person and consent the guardian to be part of the study (Appendix D: Consent). This consent process will take place with a trained interpreter. The consent will be provided in both English and Spanish. The consent will be emailed to program participants prior to the

¹⁵ Bryant, M. J., Ward, D. S., Hales, D., Vaughn, A., Tabak, R. G., & Stevens, J. (2008). Reliability and validity of the Healthy Home Survey: a tool to measure factors within homes hypothesized to relate to overweight in children. *The international journal of behavioral nutrition and physical activity*, 5, 23. <https://doi.org/10.1186/1479-5868-5-23>

¹⁶ Schrempf, S., van Jaarsveld, C. H., Fisher, A., & Wardle, J. (2015). The Obesogenic Quality of the Home Environment: Associations with Diet, Physical Activity, TV Viewing, and BMI in Preschool Children. *PloS one*, 10(8), e0134490. <https://doi.org/10.1371/journal.pone.0134490>

¹⁷ Kininmonth, A. R., Schrempf, S., Smith, A., Dye, L., Lawton, C., Fisher, A., Llewellyn, C., & Fildes, A. (2021). The Home Environment Interview and associations with energy balance behaviours and body weight in school-aged children - a feasibility, reliability, and validity study. *The international journal of behavioral nutrition and physical activity*, 18(1), 167. <https://doi.org/10.1186/s12966-021-01235-3>

consent conversation when possible. Whether consent occurs virtually or in person, a hard copy of the consent will be printed and stored by the Inova PI. A copy of the consent will be given to the guardian.

3.6. Monitoring Subjects and Criteria for Withdrawal of Subjects from the Study.

Study participants may leave the study at any time, without penalty. In some cases, the participant may be withdrawn if the HWNV physician PI determines that the study intervention is too burdensome for the participant or is adversely affecting the study participant's health. If any study participant leaves the study or is withdrawn from the study, their data will not be used in analysis.

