4.2. Method of Data Analysis

Analyses will follow the intention-to-treat principle, which categorizes participants by their treatment assignments regardless of adherence to the intervention or incomplete follow-up, and includes them in all analyses. Descriptive statistics will be calculated and reported as mean, standard deviation and 95% confidence intervals for continuous variables and frequency and percentage for categorical variables. Characteristics of study participants will be compared at baseline between the intervention and control groups and tested for significance using the two-sample t-test for continuous variables and the Chi-square test for categorical variables. Comparisons that are significant at the $P<0.10$ level will be considered for inclusion in multivariable models for primary and secondary analyses given that participants will not be randomized to their respective treatment groups.

Primary analyses will examine diet quality, screen time, physical activity, and guardian self-efficacy and confidence of those in the intervention and control groups while controlling for the correlated nature of the repeated measures within participants (i.e. baseline, post-intervention, and 6-month post-intervention). Secondary analyses will compare the BMI of guardians and BMI percentile of children at the three time points between the intervention and control groups. A longitudinal data analysis strategy will be employed with generalized estimating equations with robust CIs for both primary and secondary outcomes (Albert, 1999; Ma et al., 2012). A 2-sided p-value <0.05 will be accepted to indicate statistical significance. Additional analyses will be conducted to determine if results were influenced by other covariates including demographics (age, gender, educational attainment of guardian, income, etc.). All analyses will be conducted in SAS version 9.2.

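### Guardian BMI is compared between self-selected arms of 25, but nothing says how pregnancy is recorded or how BMI measured during or soon after pregnancy is handled

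*Combined protocol and SAP*

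**What the plan says.** - **Pregnancy is foreseen.** Section 2.5.4 says of guardians: "It is possible that some of these guardians may be pregnant at the time of consent or become pregnant during the study". It then treats pregnancy only as a question of risk, which it calls minimal.
- **Pregnancy is not excluded.** The only medical exclusion in section 2.8 applies when "the study PI determines that the intervention may exacerbate existing medical conditions of the child or the family".
- **Guardian BMI is an outcome.** Section 3.4.3 lists "BMI percentile of children and guardians enrolled in the study", measured at each office visit. Section 4.2 states: "Secondary analyses will compare the BMI of guardians and BMI percentile of children at the three time points between the intervention and control groups".
- **Who is analysed.** Section 4.2 follows intention to treat: participants are kept "regardless of adherence to the intervention or incomplete follow-up, and includes them in all analyses". Section 3.6 says otherwise: "If any study participant leaves the study or is withdrawn from the study, their data will not be used in analysis".
- **Covariates.** Baseline characteristics that differ at P<0.10 "will be considered for inclusion in multivariable models for primary and secondary analyses". Further analyses look at "other covariates including demographics (age, gender, educational attainment of guardian, income, etc". Pregnancy is not named.
- **Allocation.** Families choose their group (section 2.6) and there is no randomization (section 3.3).
- **Survey.** Appendix C has no pregnancy item. The nearest is a household-level question about health conditions that affect diet or activity.

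**The concern.** BMI during pregnancy and in the months after delivery moves for reasons unrelated to the intervention. A guardian who conceives or is in mid-pregnancy shows a gain, and one who delivers during follow-up shows a fall, so the distortion can run in either direction. With 25 guardians per arm, one or two such values carry weight in a mean. Because families choose their arm, and pregnancy could plausibly affect whether a family takes on a 12-week programme, balance between arms cannot be assumed. Even balanced cases add noise.

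If status is not recorded, the analyst cannot reliably find these values later. If it is known only informally, any decision to drop values would be made after the data are seen, in a small non-randomized comparison.

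**Working it through.** **Does any rule in the plan deal with the problem?**

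- Section 4.2 keeps everyone; section 3.6 drops those who leave or are withdrawn. The two need reconciling, but pregnancy is not a stated reason for withdrawal, so a pregnant guardian who stays is counted under either.
- The P<0.10 screen uses baseline characteristics and cannot see a pregnancy that starts later. Even if baseline pregnancy were recorded, 2 of 25 against 0 of 25 gives chi-square = 50 × (2×25 − 23×0)² / (25 × 25 × 2 × 48) = 2.08, P about 0.15, which fails the screen.

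**What size could it be?** The plan gives no power, effect size, SD or pregnancy rate, so there is no figure to reproduce beyond 25 per arm. The inputs below are assumptions.

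- Weight change 5 to 12 kg at height 1.55 to 1.60 m. BMI change G = kg / height²: 5/1.60² = 1.95 and 12/1.55² = 4.99, so G is about 2 to 5.
- SD of BMI change (s) 0.8 to 1.2.

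*Shift in the arm difference*, k cases in one arm and none in the other: kG/25.

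- k = 1: 2/25 = 0.08 to 5/25 = 0.20.
- k = 2: 4/25 = 0.16 to 10/25 = 0.40.

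*Standard error without pregnancies*: s√(2/25) = 0.226 (s = 0.8) to 0.339 (s = 1.2).

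- k = 1: 0.08/0.339 = 0.24 to 0.20/0.226 = 0.88.
- k = 2: 0.16/0.339 = 0.47 to 0.40/0.226 = 1.77.

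*Inflated standard error.* The shifted values raise the variance in their arm by k(1 − k/25)G²/24, which is 0.040G² for k = 1 and 0.0767G² for k = 2. The standard error is multiplied by √(1 + added variance/(2s²)).

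- Smallest (k = 1, G = 2, s = 1.2): √(1 + 0.16/2.88) = 1.03.
- Largest (k = 2, G = 5, s = 0.8): √(1 + 1.917/1.28) = 1.58.
- Against the inflated standard error the shift is 0.23 to 0.66 for one case and 0.45 to 1.12 for two.

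*False positives* (20,000 simulated t-tests per scenario, s = 1.0, no true effect): about 5% for one case against none, 6% to 9% for two against none, 9% to 17% for three against none.

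*Power without systematic imbalance.* If each guardian has probability p of an affected value, the variance rises by p(1 − p)G². With s = 1.0 and a true difference of 0.8, power falls from 81% to 78% (p = 2%, G = 2), 61% (p = 5%, G = 3.5) or 35% (p = 10%, G = 5).

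*Chance of at least one case* among 50 guardians, if all are women: 1 − (1 − p)^50 = 64% at p = 2%, 92% at 5% and 99% at 10%.

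*If BMI levels are compared instead of changes*, with an assumed SD of 4 to 6, the standard error is 1.13 to 1.70. One case is then 0.05 to 0.18 standard errors and two at most 0.35.

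**The case against.** Three stronger readings are tempting, and the document does not support them.

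- *That the trial expects pregnant guardians.* Section 2.5.4 says only that pregnancy is possible, in a risk discussion, and gives no rate.
- *That the plan forbids setting these values aside.* The intention-to-treat sentence settles who is analysed and in which group. It does not say that every measurement is valid, and it does not bar setting one BMI value to missing. Section 3.6 also contradicts the idea that everybody is kept.
- *That pregnancy would swamp the comparison.* One case stays below one standard error and leaves the false-positive rate at about 5%. The top of each range needs the largest weight change within the measurement window and the smallest SD. Section 4.2 does not define a change score, and on levels the effect is much smaller.

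It is also fair to say that Appendix C is described as an example that may be altered, that parents are clients of the clinic, and that BMI is taken there by a medical assistant or physician. Pregnancy may therefore be known at the visit. What can be said is that no plan to record or extract it is stated.

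Finally, this is one secondary outcome in a pilot that openly accepts selection bias. That limits the weight of the point. It does not remove the gap: no section says what to do with an affected value.

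**Conclusion.** The point holds as a gap in recording and analysis rules. Followed as written, the plan puts pregnancy-related BMI gain, or the fall after delivery, into the guardian BMI comparison. On the assumed inputs, two cases in the same arm shift the difference by up to about 1.1 inflated standard errors, one case by clearly less, and the comparison also loses precision. These figures depend on the assumed weight change, SD and number of cases, and they shrink if BMI levels are analysed. The survey-based primary outcomes and child BMI percentile are outside this point. It is an inexpensive improvement that should be made, not a threat to the trial's main conclusions.

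**What to change.** - Record pregnancy and recent delivery at each visit where guardian BMI is measured.
- In section 4.2, prespecify that guardian BMI values taken during pregnancy, or within a postpartum window whose length the investigators state in advance, are set to missing for the guardian BMI analysis only.
- Keep these families in all survey and child analyses.
- Report the number of affected guardians by arm, and add a sensitivity analysis with all guardian BMI values.
- At the same time, reconcile sections 3.6 and 4.2 on leavers, the guardian endpoint (BMI percentile in 3.4.3, BMI in 4.2), and follow-up (6 months in total in 2.3, a last measurement 6 months after the intervention in 4.2). Follow-up length governs how much pregnancy-related change can accrue.

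The cost is one data field, a short addition to 4.2 and a few lost values. Losing three guardians from one arm (22 against 25) moves the difference detectable at 80% power from 2.80 × √(2/25) = 0.79 SD to 2.80 × √(1/22 + 1/25) = 0.82 SD.
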